3.3 Exploratory Objective(s)

(1) **Objective:** To determine whether increased baseline TMB, other deficiencies in DNA damage repair mechanisms and PD-L1 expression correlate with FATSI negativity, and if these findings are independently associated with response to therapy.

[figure not shown]

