(95% CI: 6.5 to 20.4%), including three complete responses and nine partial responses. All 12 responses were in patients with PDL-1 positive tumors, for an overall response rate of 14.6% (95% CI, 7.8 to 24.2%). The estimated median response duration was not reached (range ≥ 3.7 to ≥ 18.6 months). Treatment related grade 3 to 4 adverse events (diarrhea, asthenia, pyrexia, arthralgias and increase in AST) occurred in 12.2% of patients.

PARP inhibition has been evaluated in several randomized controlled trials. Olaparib was evaluated in two randomized, placebo-controlled double-blind, multi-center studies in patients with recurrent ovarian cancers who were in response to platinum-based therapy. SOLO-2 evaluated patients with a gBRCAm, who had a response to platinum based therapy. These patients were then randomized to maintenance therapy with olaparib. The patient who received olaparib had a PFS 19.1 months compared to 5.5 months in the control arm [Pujade-Lauraine et al., 2017]. STUDY 19 also evaluated olaparib as maintenance therapy for recurrent ovarian cancer, regardless of BRCA status and also demonstrated a PFS advantage to those women receiving olaparib maintenance [Ledermann et al., 2012]. The POLO trial evaluated olaparib for gBRCAm metastatic pancreatic cancer [Golan et al, 2019]. Maintenance olaparib demonstrated a longer PFS for this cohort of pancreatic cancer patients.

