7.0 STATISTICAL ANALYSIS PLAN

7.1 Statistical Analysis Plan Summary

7.2 Statistical Analysis Plan

Sample size calculation: Single-Stage design will be used for this study [A'Hern, 2001; Fleming, 1982]. The study will require 48 subjects to decide whether the proportion responding (P), is less than or equal to 0.130 or greater than or equal to 0.280. If the number of responses is 10 or more, the hypothesis that $P \leq 0.130$ is rejected with a target error rate of 0.100 and an actual error rate of 0.087. If the number of responses is nine or less, the hypothesis that $P \geq 0.280$ is rejected with a target error rate of 0.100 and an actual error rate of 0.099.

Efficacy analyses: The iORR will be defined as the proportion of patients with an “immune” complete response (iCR) or “immune” partial response (iPR). For the primary iORR analysis in all the treated population, patients with an iCR or iPR will be counted as successes and all other patients (including those with missing response information) will be counted as failures. The percentage of iORR with its 95% confidence interval (CI) will be presented.

Progression free survival (PFS) will be defined among all treated patients as the time from first dose of study drug until the first date of either disease progression or death due to any cause. The date of disease progression will be defined as the earliest date of disease progression based on central review. For patients whose disease has not progressed at the time of the analysis, censoring will be performed using the date of the last valid disease assessment. The data will be analyzed by the Kaplan-Meier method. The median PFS time and 95% CI will be recorded.

Overall survival (OS): Median OS will be defined as the time from the beginning of study drug treatment until death due to any cause. For patients who have not died at the time of the analysis, censoring will be performed using the date the patient was last known to be alive. The data will be analyzed by the Kaplan-Meier method. The median OS and 95% CI will be recorded.

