Safety analyses: Safety analyses will be presented descriptively. The focus of adverse event (AE) summarization will be on treatment-emergent adverse event (TEAEs). A TEAE is defined as an AE that occurs or worsens in the period extending from the first dose of study drug to 30 days after the last dose of study drug in this study. TEAEs will be summarized and summary tables will be created to show the number of patients reporting TEAEs by severity grade and corresponding percentages. A patient who reports multiple TEAEs within the same Preferred Term (or System Organ Class) is counted only once for that Preferred Term (or System Organ Class) using the worst severity grade. Separate summaries will be prepared for TEAEs classified as severe or life threatening (Grade 3 or higher); study drug-related AEs; AEs leading to treatment interruption, modification, or discontinuation; serious AEs; and death. Dose interruptions, reductions, and relative dose intensity will also be summarized.

All results including efficacy, PFS, OS and safety analysis will also be reported based on race/ethnicity stratification.

FATSI analysis will be conducted in batches. We expect that similar to mismatch repair deficient patients, the immune-related objective response will be at or above 40% in patients with functional FA deficiency (FATSI negative), and less than 10% in patients without either homologous recombination repair

deficiency or mismatch repair deficiency. Based on our prior screening data, we anticipate that close to 30% of patients will be FA functionally deficient.

Total enrollment of 48 patients is planned. We will report the 90% confidence interval estimates of iORR both overall and by FATSI status using the exact method (Clopper Pearson). However, the planned study is small for a well powered comparison given that we expect only 15 FATSI-negative patients. Instead, variation in iORR by FATSI status will be assessed by considering the one-sided 95% lower confidence limit (95%LCL) for the difference. As an example, an observed increase in iORR for FATSI- patients of 30.9%, based on 6 out of 15 FATSI- responders compared with 3 out of 33 FATSI+ responders, provides 95% confidence that the true increase for patients with FA deficient tumors is at least 7.1%, suggesting that further study of pembrolizumab/olaparib in FA deficient cervical cancer patients is warranted.

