Kaplan-Meier curves will be used to estimate the distributions of overall survival and immune-related progression-free survival (iPFS). Point estimates and 2-sided 95% confidence intervals will be reported for selected times using Greenwood's variance and the log-log transform method. This will include the 20-week iPFS for purposes of comparison. Based on the panel sequencing results, somatic alterations will be summarized and reported as proportions for genes in FA competent and FA functionally deficient tumors. Confidence intervals will be calculated using the exact method. Additional analyses will be done to establish relationships between treatment and certain baseline characteristics, including deficiencies in the FA pathway, PD-L1 expression, TMB, other deficiencies in DNA damage repair mechanisms. These relationships will be explored primarily through logistic regression or cox proportional hazards regression, depending on the outcome of interest.

For known or predicted deleterious mutations of suspected inheritance trait detected during the trial, the process would be aided by making sure that patients carrying these mutations get referred for genetic counseling and CLIA certified germline analysis. The Miami Cancer Institute has these services readily available.

Stool Microbiome Data Analyses: Centered log-ratio (CLR) transformations will be applied to microbiome data. Log-ratios make the data symmetric and linearly related, and places the data in a log-ratio coordinate space. Thus, we can obtain information about the log-ratio abundances of features relative to other features in the compositional dataset. Zero counts of operational taxonomic units (OTU) will be converted to a probability vector prior to centered log-ratio transformation. Aitchison distance, which is simply the Euclidian distance between samples after CLR transformation, and the distances between samples same as the phylogenetic isometric log-ratio (ILR), will be calculated and used for clustering and ordination. Compositional principal component analysis (PCA) will be applied and biplots will be used to display the relationships between OTUs and the distances between samples.

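### The biomarker-response models use logistic regression with no sparse-data method, although only about 9 to 10 responders are expected among 48 patients

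*Combined protocol and SAP*

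**What the plan says.** Section 3.3 sets an exploratory objective. It asks whether TMB, other DNA-repair defects and PD-L1 correlate with FATSI negativity, and "if these findings are independently associated with response to therapy". Section 4.2.3.2 repeats this and adds MSI. The word independently implies a model with several predictors.

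Section 7.2 lists four baseline factors: FA-pathway deficiency, PD-L1 expression, TMB and other repair defects. It then states: "These relationships will be explored primarily through logistic regression or cox proportional hazards regression, depending on the outcome of interest". Read literally, the preceding sentence relates these factors to treatment, which a single-arm trial cannot estimate; section 3.3 shows that response is meant. No coding of PD-L1 or TMB is given, nor any covariate limit or rule for empty cells. Penalised logistic and survival models are specified later in 7.2, but only for the microbiome data.

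The separate FATSI analysis in 7.2, which serves the third secondary objective in 3.2, is unadjusted: "variation in iORR by FATSI status will be assessed by considering the one-sided 95% lower confidence limit (95%LCL) for the difference". PD-L1 positivity is not an entry criterion (4.2.1). On the cited pembrolizumab monotherapy cohort, section 4.1.1 reports: "All 12 responses were in patients with PDL-1 positive tumors".

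**The concern.** Maximum-likelihood logistic regression behaves badly when events are few. If every patient at one level of a binary predictor is a non-responder, the estimate for that predictor does not exist and software returns a huge odds ratio with a meaningless Wald interval. Where estimates do exist, they tend to lie too far from zero.

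This regression is the only planned analysis that can say whether FATSI carries information beyond PD-L1. If the model fails and no rule was set beforehand, the analyst must drop markers, recode them or change method after seeing the data. The unadjusted FATSI limit cannot fill the gap, because any imbalance in PD-L1 between FATSI groups passes straight into it.

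**Working it through.** **Design figures.** Section 7.2 states: "The study will require 48 subjects to decide whether the proportion responding (P), is less than or equal to 0.130". The alternative rate is 0.28, and the boundary is 10 or more responses. With X ~ Binomial(48, p), P(X ≥ 10 | p = 0.13) = 0.087 and P(X ≤ 9 | p = 0.28) = 0.099. Both match the stated error rates.

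**Expected responders.**
- At the null rate: 48 × 0.13 = 6.2
- FATSI example in 7.2: 6 of 15 plus 3 of 33 = 9
- At the success boundary: 10
- At the alternative: 48 × 0.28 = 13.4

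**Responders per predictor.** Four factors are named in 7.2, or five if MSI is counted separately. This gives 9/4 = 2.25, 10/4 = 2.5 and 10/5 = 2.0. With four factors, the range over the design's response rates is 6.2/4 = 1.6 to 13.4/4 = 3.4.

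**Empty PD-L1 cell.** Section 4.1.1 gives 82 of 98 patients with CPS ≥ 1, so 16/98 = 16.3% had CPS < 1. If the same mix enrols (an assumption), 0.163 × 48 is about 8 patients. If PD-L1 is coded CPS ≥ 1 versus < 1 (also an assumption), P(none of 8 responds) = (1 − q)^8:

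| True response rate q in CPS < 1 | P(no responder) |
|---|---|
| 5% | 66% |
| 10% | 43% |
| 13% | 33% |
| 18.75% (= 9/48) | 19% |
| 28% | 7% |

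The cited cohort had 12 responses, all in the 82 PD-L1-positive patients, hence 0 of 16 in the rest. The exact 95% upper limit is 1 − 0.025^(1/16) = 20.6%, so most of this table is compatible with it.

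**Simulation, binary markers.** n = 48; iORR about 40% in FATSI-negative and 10% in FATSI-positive patients; PD-L1 positivity 82/98; PD-L1 odds ratio 1 to 3. Share of trials with at least one infinite odds ratio:
- FATSI + PD-L1: 27-55%
- plus one marker at 10% prevalence: 52-74%
- plus three markers at 20%, 10% and 25%: 64-78%

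The marker prevalences are assumptions. The rates move by a few points between simulation set-ups.

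**Simulation, continuous TMB.** FATSI + PD-L1 + TMB, with 15 FATSI-negative and 8 PD-L1-negative patients, true FATSI odds ratio (0.40/0.60)/(0.0909/0.9091) = 6.67 (log 1.90), and TMB log odds ratio 0.5 per SD (assumed). Share with an infinite estimate:

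| Expected responders | PD-L1 OR 1 | PD-L1 OR 3 |
|---|---|---|
| 6 | 40% | 63% |
| 10 | 18% | 43% |
| 13 | 7% | 28% |

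**Bias.** At 10 responders in this model, finite fits had a mean FATSI log odds ratio of 2.12-2.13, an odds ratio of about 8.4 against 6.7, so about 25% too high. With an added marker at 10% prevalence the mean was 2.21, or about 9.1. Firth estimates on the same data averaged 1.88-1.91 in the three-term model, against a true 1.90. Inflation is not uniform: with a true PD-L1 log odds ratio of 1.10, the finite fits averaged only 0.55, because trials with an empty cell drop out. Firth gave 0.92.

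**Unadjusted FATSI limit, bounding case.** Suppose FATSI has no effect, CPS ≥ 1 patients respond at 25% and CPS < 1 patients at 0%. If all 8 CPS < 1 patients are FATSI-positive, the rates are 25% versus 25 × 0.25/33 = 19%. The chance that a Newcombe one-sided 95% lower limit exceeds zero is then 12.4%, against 5.2% when PD-L1 has no effect. That allocation has probability C(33,8)/C(48,8) = 3.7% if PD-L1 and FATSI are independent. With 1, 2 or 3 of the 8 FATSI-negative (proportional is 8 × 15/48 = 2.5), the chance is 8.8%, 5.9% or 3.8%.

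**The case against.** The strongest reply is that the plan labels this work exploratory, says the relationships will be explored rather than tested, and concedes that the trial is small for a well-powered FATSI comparison. The word primarily leaves room for other methods, and an infinite odds ratio is obvious to any analyst. All of that lowers the stakes. It does not make the stated method suitable, and it leaves the choice of replacement until after the data are seen.

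It is also fair that the divergence rates rest on assumed prevalences and on binary coding, neither of which the plan gives. With continuous TMB, and PD-L1 having no effect, the rate at 10 responders is 18%.

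Some stronger readings are tempting but unsupported:
- A reader might infer that PD-L1-negative patients are expected to have no responders. The documents do not say so. The 0 of 16 comes from monotherapy, this trial adds olaparib to raise efficacy, and the plan's 9 of 48 implies 8 × 9/48 = 1.5 responders in that group if PD-L1 and FATSI are independent.
- A reader might infer that the plan expects PD-L1 to track FATSI negativity. Sections 3.3 and 4.2.3.2 pose that as an open question, so confounding of the FATSI limit is a possibility, and the 12.4% above is a worst case.
- A reader might extend the criticism to the Cox models. Nothing here supports that; progression and death events should outnumber responses.

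**Conclusion.** The point holds as a gap in method. With about 9 to 10 responders, the logistic models described in 7.2 will fail to give a finite answer in a substantial share of trials: about 27-55% for FATSI with binary PD-L1, about 50-78% with one to three further uncommon binary markers, and 18-43% with continuous TMB instead. Finite FATSI odds ratios tend to be about 10-25% too high in the two- and three-term models, and more with a rare marker added. These sizes depend on the cited cohort's PD-L1 mix, CPS ≥ 1 coding, PD-L1 odds ratios of 1 to 3 and assumed marker prevalences of 10-25%. An empty PD-L1-negative cell is plausible, not expected.

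The consequence is confined to the exploratory biomarker conclusions and to how the secondary FATSI result is interpreted. The primary iORR analysis, the sample size and the 10-responder rule are unaffected.

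**What to change.** In 7.2, for the biomarker-response models:
- Replace ordinary logistic regression with Firth-penalised logistic regression and profile-likelihood intervals.
- Preferably pre-specify FATSI plus PD-L1 as the main multivariable response model, with the other markers in supporting models.
- State how PD-L1 and TMB are coded. The stratified analysis below needs a PD-L1 cut-point; CPS ≥ 1 is the one used in the background sections.
- Beside the unadjusted FATSI lower limit, report the PD-L1-stratified (Mantel-Haenszel) difference in iORR as a sensitivity result. It remains computable when a cell is empty.

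The Cox models can stay as they are. The cost is a few sentences of SAP text, standard software and one extra table row. The downside is slightly shrunken estimates. Penalisation gives finite, better-centred estimates but adds no information, so intervals will remain wide.

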8.0 LABELING, PACKAGING, STORAGE AND RETURN OF CLINICAL SUPPLIES

8.1 Investigational Product

The investigator shall take responsibility for and shall take all steps to maintain appropriate records and ensure appropriate supply, storage, handling, distribution and usage of investigational product in accordance with the protocol and any applicable laws and regulations.

Pembrolizumab and olaparib will be provided by Merck as summarized in Table 15.

Table 15 Product Descriptions

Product Name & Potency	Dosage Form
Pembrolizumab 100 mg/ 4mL	Solution for Injection
Olaparib 100 and 150 mg tablets	Oral

8.2 Packaging and Labeling Information

Supplies will be labeled in accordance with regulatory requirements.

8.3 Clinical Supplies Disclosure

This trial is open-label; therefore, the participant, the trial site personnel, the Sponsor and/or designee are not blinded to treatment. Drug identity (name, strength) is included in the label text; random code/disclosure envelopes or lists are not provided.

8.4 Storage and Handling Requirements

Clinical supplies must be stored in a secure, limited-access location under the storage conditions specified on the label.

Receipt and dispensing of trial medication must be recorded by an authorized person at the trial site.

Clinical supplies may not be used for any purpose other than that stated in the protocol.

8.5 Returns and Reconciliation

The Miami Cancer Institute has a dedicated Investigational Drug Service (IDS), including a dedicated IDS Supervisor who leads the coordination of investigational drugs services for clinical research at Miami Cancer Institute (including inventory and receipt as detailed below).

Investigational Drug Services (IDS) Supervisor:

[name], Pharm D, BCOP
[name]
[name]
Office: [contact]
Email: [contact]

The IDS team provides required pharmacy services for investigational drug studies including oversight of drug storage, handling, preparation, deposition, medication dosing, staff education, and other related activities. All pharmacists involved in the compounding of investigational products are trained on each individual protocol in regards to receipt, preparation, storage, dispensing and administration, product reconciliation and source documentation. Additionally, all pharmacists involved in the compounding aspect are CITI trained and listed on the delegation of authority.

- Disposition and/or destruction of IPs following drug accountability are performed according to specific instructions provided by the sponsor and/or protocol. Disposal and/or destruction of investigational products on-site are performed in accordance with BHM BCH administrative policy
- All products will be disposed of according to regulatory requirements according to institutional policy and in accordance with the Environmental Protection Agency and the State of Florida Department of Transportation (DOT) regulations for hazardous and non-hazardous pharmaceutical waste.
- Disposition of the investigational product must be witnessed by two members of the research team and documented per institutional policy
- Documentation of IDS accountability will be performed from the time of initial product receipt through the destruction or return of the product to the supplier

The investigator is responsible for keeping accurate records of the clinical supplies received from Merck or designee, the amount dispensed to and returned by the participants and the amount remaining at the conclusion of the trial.

Upon completion or termination of the study, all unused and/or partially used investigational product will be destroyed at the site per institutional policy. It is the Investigator's responsibility to arrange for disposal of all empty containers, provided that procedures for proper disposal have been established according to applicable federal, state, local and institutional guidelines and procedures, and provided that appropriate records of disposal are kept.

9.0 ADMINISTRATIVE AND REGULATORY DETAILS

9.0.1 Confidentiality of Data

Both the investigator and the Sponsor affirm that information regarding this trial will be maintained in confidence, and such information will be divulged to the institutional review board, ethics review committee (IRB) or similar or expert committee; affiliated institution and employees, only under an appropriate understanding of confidentiality with such board or committee, affiliated institution and employees. Data generated by this trial will be considered confidential by the Sponsor and the investigator.

9.0.2 Confidentiality of Subject Records

The investigator agrees that the IRB or regulatory authority representatives may consult and/or copy trial documents in order to verify worksheet/case report form data. By signing the consent form, the subject agrees to this process. If trial documents will be photocopied during the process of verifying worksheet/case report form information, the subject will be identified by unique code only; full names/initials will be masked prior to transmission to the Sponsor.

The investigator and Sponsor agree to treat all subject data used and disclosed in connection with this trial in accordance with all applicable privacy laws, rules and regulations.

9.0.3 Confidentiality of Investigator Information

The investigator recognizes that certain personal identifying information with respect to the investigator, and all sub-investigators and trial site personnel, may be used and disclosed for trial management purposes, as part of a regulatory submission, and as required by law. This information may include:

1. Name, address, telephone number and e-mail address;
2. Hospital or clinic address and telephone number;
3. Curriculum vitae or other summary of qualifications and credentials; and
4. Other professional documentation.

Consistent with the purposes described above, this information may be transmitted to the Sponsor, and subsidiaries, affiliates and agents of the Sponsor, in your country and other countries, including countries that do not have laws protecting such information. Additionally, the investigator's name and business contact information may be included when reporting certain serious adverse events to regulatory authorities or to other investigators. By signing this protocol, the investigator expressly consents to these uses and disclosures.

9.0.4 Confidentiality of IRB Information

The Sponsor is required to record the name and address of each IRB that reviews and approves this trial. The Sponsor is also required to document that each IRB meets regulatory and ICH GCP requirements by requesting and maintaining records of the names and qualifications of the IRB members and to make these records available for regulatory agency review upon request by those agencies.

